These instruments will be used to assess comparability among groups at baseline and to assess any changes in response to the interventions. The General Well Being Scale measures overall attitudes and quality of life; the Hassles Scale assesses the frequency and intensity of "hassles" or irritants ranging from minor annoyances to fairly major problems; the Multidimensional Health Locus of Control Scale assesses the extent to which participants perceive that their behavior influences their health; and the Treatment Evaluation Scale assesses treatment credibility and efficacy as well as outcome expectancy. All these forms will be administered study-wide except the Treatment Evaluation Scale, which will be administered to all subjects except those in the lifestyle interventions comparison group.

7. Demographic Information and Participant Contact Information

The demographic data will be used in the analyses for stratification purposes. The participant contact information will be used exclusively by the clinics and will be updated at mid-trial.

8. Food Frequency and 24-Hour Diet Recall Data

Dietary data will be used to characterize baseline intake and to assess dietary change over time. In addition, diet recall data may be used by the interventionists to provide feedback to participants in the dietary intervention groups. Completion of the food frequency questionnaire during screening will serve as a behavioral compliance measure at all clinics for eligibility purposes.

9. Blood and Urine Samples

Blood samples collected during screening will be split so that eligibility tests (serum creatinine, potassium, calcium, cholesterol, and glucose) can

be performed at a local laboratory and baseline measurements can be determined at a central laboratory. Blood samples collected during follow-up will be used primarily for compliance assessment and safety monitoring.

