Measures of secondary endpoints relevant to the stress management intervention include both study-wide and intervention-specific instruments. Among the former are the Lazarus' Hassles Scale, a Treatment Evaluation scale (not given to Lifesytle controls), the Multidimensional Health Locus of Control, and Ware's Psychological General Well Being Scale. The intervention-specific forms include a Stress Management Activities Scale, Siegel's Multidimensional Anger Inventory, the Framingham Anger Subscale, and Lazarus' Uplifts Scale. Cardiovascular reactivity testing will also be done. These intervention-specific measures will be obtained from all members of the active stress intervention group, about 80% of the lifestyle controls, and 20% of those in the other active intervention at each center offering stress management.

4. Supplements

Secondary endpoints used for the supplements arm of the trial will provide an indication of changes in the levels of intake of the supplements over the course of the trial. For magnesium, both urine (based on 24-hour specimens) and serum levels will be assessed, while for potassium, urine levels only will be a secondary endpoint. Similarly, urine calcium will serve as a secondary endpoint for the calcium supplemented group and plasma fatty acid phospholipids for the fish oil supplemented group. Total and HDL cholesterol may serve as secondary endpoints, pending allocation of funds. Because of the expense of analyzing the fatty acid phospholipids, they will be collected on all participants and controls at baseline, 3 months and 6 months, but analyzed only on a 50% sample of these groups at 3 months and 6 months (termination). The analyzed data collection schedules for the laboratory tests for all the supplements groups are summarized in Table 5.

SAFETY MONITORING

The non-pharmacologic interventions being tested in TOHP are all moderate and of a level that is encountered frequently among free-living populations. Moreover, the eligibility and exclusion criteria for the trial have been designed

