to exclude any individuals who are at particular risk, such as those with preexisting conditions that might make participation difficult or contraindicated. Specifically, those with a history of heart disease, cancer, renal disease, diabetes, chronic gastrointestinal problems, physical handicaps that would affect participation in an exercise program, high cholesterol, and elevated serum potassium or calcium will not be permitted to enroll in TOHP. Nonetheless, there are certain parameters that will be monitored throughout the study period.

The chief safety consideration relates to individuals who may become hypertensive during the follow-up period of the trial. Clinic personnel will be instructed to implement the following procedures whenever a set of BP readings falls in the hypertensive range. A BP level that would raise the possibility of termination is a true DBP of 95 mm Hg or greater as determined by the mean of nine separate readings. Thus, if a subject's mean DBP at any single monitoring visit is greater than or equal to 93.5 (the sum of three readings greater than or equal to 281 mm Hg), that individual will be asked to return for a second visit at least one week later, at which time three additional readings will be taken. If the mean of these six readings over two visits is less than 93.5 mm Hg, the participant will be continued in the study. If, on the other hand, the mean of the six readings is 93.5 mm Hg or greater (the sum of six readings greater than or equal to 561), then the subject will be asked to return in a minimum of one week for a third set of BP measurements. At that time, if the mean DBP over nine readings is greater than or equal to 95 mm Hg (the sum of nine readings greater than or equal to 855 mm Hg), then that participant will be terminated from the study. Note that if the second or third set of three readings comprising this set of nine safety monitor readings averages 93.5 or greater, the cycle is not started again. In other words, one set of three readings triggers the collection of the set of nine safety monitoring readings, and it is the result (sum or average) of that set of nine BPs that is the basis for any future action.

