Although the level of exercise being prescribed as part of the weight loss intervention program is very moderate, as an added safety precaution, all individuals assigned to that group will undergo submaximal bicycle ergometer testing to identify participants who may need to obtain permission from their physicians before beginning the exercise component. In addition, the bicycle ergometer test will be used among both weight loss program participants and high-weight lifestyle controls as a measure of compliance with the exercise regimen. Precautions taken at the clinic to ensure the safety of these individuals include identifying those who are at increased risk of a cardiovascular event, performing a resting ECG on such persons for review by a physician, and monitoring them more closely during the test. Each clinic will have staff members certified in cardiopulmonary resuscitation available at the test site as well as ready access to an ambulance and trained emergency teams.

Other variables to be monitored periodically as a safety precaution include serum creatinine, serum potassium, and serum magnesium. All follow-up forms will also collect information on possible side effects of the interventions, such as fatigue, faintness, skin rash, or diarrhea. In addition, at each follow-up visit, participants will be asked about their current status with respect to all of the medical conditions that constituted exclusions from the trial, including pregnancy, and a positive response may raise the possibility of early termination from intervention.

QUALITY CONTROL

Quality control of all training, intervention, data collection, and data processing procedures for TOHP is essential to the ultimate success of the trial. There are several basic principles underlying the approach to quality control that has been adopted.

- 1. Standardization of measurements and interventions through certification and recertification of study personnel.
- 2. Use of clear and specific protocols for all study activities, including training for all aspects of the trial, data collection, interventions, equipment maintenance, and data processing.
- 3. Validation and verification of all data collection and data management procedures through double entry and checking, followed by random checking of a sample by a third person or computer program.

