At SV3 only, to be collected and stored for all lifestyle participants at clinics offering weight loss. At the 12 and 18 month follow-up visits, to be collected and stored for weight loss and high weight control groups only (central laboratory)

d
To be collected and stored at the central lab for all lifestyle and control
participants, with a sample of sodium, stress, and control groups to be analyzed,
pending availability of funds

Table 5

BLOOD AND URINE TESTS FOR SUPPLEMENTS INTERVENTIONS

	Š	Stage 1 (Ca	1 (Calcium and Magnesium) FOLLOW-UP VISI	and Magnesium) FOLLOW-UP VISITS	ge 2 eline	nd Fi OW-UP	ii)
BLOOD Sorum calcium	SV3	SRV	3-Month	6-Month	EL3 Xa	3-Month 6-Month	uth .
Serum glucose	m×						
Serum creatinine	×a				×a		
Serum potassium	×				×a		
Serum magnesium	×		×q	×q			
Total cholesterol	×				e ×		
Plasma and serum samples*	×						
Plasma fatty acid phospholipids	ds	-	-		×	×°°×	-
Plasma sample for possible lipid analyses					×	q ^X q ^X	
URINE Creatinine	×	×	×	×	×	×	
Sodium	×	×	×	×	*	×	
Potassium	×	×	×	×	×	× ×	
Magnesium	×	×	рx	px			
Calcium	×	×	×e	×e			
a For eligibility (local labou	laboratory)		N W	Note: All of the all participants	of the above plasma and pants in the supplements	serum samples	are drawn

a For eligibility (local laboratory)
b Fish oil and control groups only
c 50% sample of fish oil and control groups only
magnesium and control groups only
c Calcium and control groups only

specific assays are performed on all or a sample of participant all participants in the supplements intervention; analyses for as described in the footnotes.

To be collected and stored for possible future analyses.

Table 6
OUTLINE OF THE LOW-SODIUM INTENSIVE INTERVENTION SESSIONS

SESSION	THEME
Individual	Welcome
Group 1	'First Taste'
Group 2	'The Big Picture'
Group 3	'Starting Early'
Group 4	'New Approaches to Lunch'
Group 5	'The Best Meal of the Day'
Individual	Problem Solving
Group 6	'Sodium and Social Life'
Group 7	'Putting it all Together'
Group 8	'Keeping up with a New Lifestyle'

Monthly Maintenance Sessions

Table 7 SCHEDULE OF INDIVIDUAL AND GROUP CONTACTS IN THE LOW SCITCH INTERVENTION

Scre	ening		Rando	mizati	.on	Inter	nsivo	Intervo	ntion	Phase			
			Weeks	:									
								~					
SV1	SV2	SV3	SRV	1	2	3	4	5	€	7	8	9	10
			INDl		CT. 7			IND2		-			
				GF1	GF I	GP3	GP4		GP 5		GPó		GP?

IND = Individual contact

.GP = Group contact

'TR	AN	SITI	ON'				MAINTE	NANCE				END
Mon	th	s:										
3		4	6 .	8	10	12	14	⁻ 16	18	2C	22	24

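### Serum potassium and creatinine are promised as periodic safety monitoring, but the laboratory schedules list them only as pre-randomization eligibility tests

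*Protocol*

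**What the plan says.** The Safety Monitoring chapter of the protocol names three serum variables: "Other variables to be monitored periodically as a safety precaution include serum creatinine, serum potassium, and serum magnesium". Earlier in that chapter, after describing the exclusions that protect participants at entry, it says: "Nonetheless, there are certain parameters that will be monitored throughout the study period". The Follow-Up Schedule chapter, under Blood and Urine Samples, agrees: "Blood samples collected during follow-up will be used primarily for compliance assessment and safety monitoring".

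The tests themselves are laid out in Table 4 (lifestyle interventions) and Table 5 (supplements). The Supplements item under secondary endpoints describes the role of Table 5: "The analyzed data collection schedules for the laboratory tests for all the supplements groups are summarized in Table 5". The rows "Serum potassium" and "Serum creatinine" appear in both tables. The entries tied to eligibility carry the footnote "a For eligibility (local laboratory". On what is measured during potassium treatment, the secondary-endpoint text says that "for potassium, urine levels only will be a secondary endpoint".

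**The concern.** The safety text and the laboratory schedule describe different studies. One has serum potassium and creatinine followed over time. The other measures them only to decide who may enter. A laboratory or clinic working from the tables would leave a stated safety measure undone.

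This matters most in Stage 2, where one arm receives 60 mmol of potassium a day for six months (Table 11). The protocol itself treats serum potassium and creatinine as relevant to safety: unexplained hyperkalemia and raised creatinine are exclusions. The Data Analyses chapter also promises safety monitoring with emphasis on the supplements. If the tables govern, the Data and Safety Monitoring Committee would receive no scheduled serum potassium or creatinine comparison between the potassium and placebo groups.

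**Working it through.** No formula applies. The check sets the promise beside the schedules, visit by visit.

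| Serum test | SV3 | Stage 1, 3 and 6 months | EL3 (before Stage 2) | Stage 2, 3 and 6 months | Lifestyle follow-up (Table 4) |
|---|---|---|---|---|---|
| Potassium | marked | none | marked, eligibility footnote | none | none |
| Creatinine | marked, eligibility footnote | none | marked, eligibility footnote | none | none |
| Magnesium | marked | marked at both | none | none | not listed |

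1. *Are the marks eligibility tests?* In the extracted Table 5 the SV3 potassium mark has no footnote. The Blood and Urine Samples text nevertheless names creatinine and potassium among the local eligibility tests at screening, and Table 4 footnotes both at SV3.

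2. *Do any marks fall during potassium treatment?* No. The Supplements section gives potassium only in Stage 2, and randomization to it follows the third re-eligibility visit. SV3 and EL3 both precede exposure. The count of scheduled on-treatment serum values is therefore 0 for potassium and 0 for creatinine, against 2 for magnesium (3 and 6 months of Stage 1).

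3. *Is blood available at the Stage 2 visits?* Table 3 schedules a blood sample at F12 and F13, the 3- and 6-month visits. At those visits Table 5 lists only plasma fatty acid phospholipids and a plasma sample for possible lipid work. The row for stored plasma and serum is marked at SV3 only.

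4. *Could the blank cells be extraction damage?* Table 5 is damaged, but the spacing of the two rows places their second mark under EL3. The cleaner Table 4 has no follow-up mark for either test. Its potassium row has a stray dash under 6 months and a stray colon under 18 months. Neither is an entry mark, and Table 2 draws no blood at 6 months. The statement that potassium is a urine-only endpoint fits the same reading.

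5. *How many people?* Table 1 estimates 207 on potassium and 203 placebo controls for Stage 2: 207 + 203 = 410. These rest on re-randomizing 85% of Stage 1 participants plus six more per group at one clinic. The 203 are shared with fish oil. If they split about evenly, as the protocol describes for Stage 1, roughly 203 / 2 ≈ 100 would take potassium placebo.

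**The case against.** Several points can fairly be made in the plan's defence.

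- *Other checks continue on treatment.* This stands. Follow-up forms collect side effects, and participants are asked at each visit about every condition that was an exclusion. Health counselors can refer to a physician, and urine potassium and creatinine are marked at the Stage 2 follow-up visits. A reader might infer that the potassium arm has no safety check at all, and the protocol does not support that. These items still do not supply the serum values that the Safety Monitoring chapter names.
- *The committee is not blind to safety.* This stands. It receives six-monthly safety analyses, including side effects in treated and placebo groups, and may suggest further analyses. A reader might infer that it would have no laboratory or safety comparison. What is missing is a scheduled serum potassium and creatinine comparison.
- *Table 5 is only a summary.* This stands in part. Two places in the text state the intention, so the table may simply have dropped two rows of entries, and the Manual of Operations is not shown. It cannot therefore be said that the tests would never be done. But the protocol offers Table 5 as the schedule of analyzed tests, and it does show follow-up entries for magnesium, which the same sentence names.
- *Participants are screened at SV3 and again at EL3.* True, but both results predate potassium exposure and cannot describe what happens under it.
- *The primary analysis is untouched.* This stands, and it limits the weight of the point.

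**Conclusion.** The contradiction is real. Serum creatinine and potassium are promised as periodic safety variables, yet Tables 4 and 5 schedule neither at any follow-up visit in the lifestyle arms, Stage 1 or Stage 2. In the comparison where it matters most, an estimated 410 participants (207 potassium, 203 shared placebo) would have no scheduled on-treatment serum value for either variable.

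The conclusion assumes that the empty cells are genuine, which the agreement of Table 4, the row spacing and the urine-only statement supports. It also assumes that no document outside the protocol adds the tests. It is an internal contradiction that should be fixed. It does not affect randomization, the primary endpoint or power. Nothing here shows which of the two, text or tables, reflects what was intended.

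**What to change.** Reconcile the Safety Monitoring statement with Tables 4 and 5. There are two consistent outcomes:

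- If the monitoring is intended, add serum potassium and serum creatinine entries at follow-up visits where a blood draw is already scheduled (F12 and F13 in Table 3 for Stage 2). State that they are for safety and in which groups they are run. First confirm that serum is collected at those visits. It is tempting to assume that the assays could use samples already held, but Table 5 lists only plasma there.
- If it is not intended, correct the sentence so that it names only what the tables schedule, and bring the sentence on the use of follow-up blood into line.

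The choice between these, the timing and any action limits are for the study clinicians.

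The cost of the first option is two assays per chosen visit and possibly one extra serum tube at an existing draw. For costing only, with full attendance and both Stage 2 follow-up visits in the potassium and placebo groups, the ceiling is 410 × 2 visits × 2 assays = 1,640 assays. No new visit is needed. The second option costs a text edit.

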Both baseline and termination DBPs are proposed as averages of 9 measurements, taken at 3 visits with 3 readings per visit. This procedure will reduce the variability of the BP measure, thus increasing the power of the study to detect true differences. The variance of the mean BP (\overline{x}) at either baseline or termination can be written as:

$$V_{(\overline{x})} = \sigma^2 = \sigma^2_p + \sigma^2_A/N + \sigma^2_e/NK$$

where: σ^2_p = between-person variance

 σ^2^{P} = between-visit variance

 σ^2 = within-visit variance

N = number of visits = 3

K = number of measurements per visit = 3

Besides these components, the variance of the change in BP will also be affected by temporal variation, or the tracking correlation over periods of time. The variance of the change from baseline (\overline{x}_1) to termination (\overline{x}_2) can be written as:

$$V(\overline{x}_1 - \overline{x}_2) = 2\sigma^2(1-\rho)$$

where ρ = the observed tracking correlation of the BP means over an average of 18 months of follow-up for the lifestyle interventions and six months of follow-up for the supplement interventions. Thus, to estimate the variance of the change in means, we need to estimate the variance components and the tracking correlation.

1. The estimated total variances for DBP in black and white males and females have been published (101). These were combined by taking weighted averages using the race and gender distribution of the Hypertension Detection and Follow-up Program (102). These average components are:

$$\sigma^{2}_{p} = 109.11$$

$$\sigma^{2}_{A} = 26.76$$

$$\sigma^{2}_{e} = 7.42$$

Therefore, $V_{(\vec{x})}$, the estimated variance of the mean DBP at baseline or termination (averaged over three visits with three readings per visit) is 118.85.

2. A study of tracking correlation of BP in Wales (103) suggests a correlation of 0.58 for DBPs taken four years apart. This was based on a single measurement at each point. Data from an industrial population (104) suggest a one-year correlation of 0.85 for an average of 12 measurements taken at four visits with three measurements per visit. The tracking correlation observed is heavily influenced by the number of visits and measurements. The relationship of observed ($\rho_{\rm obs}$) to true ($\rho_{\rm true}$) correlation is:

$$\rho_{\text{true}} = \rho_{\text{obs}} \times (\sigma^2_p + \sigma^2_A/N + \sigma^2_e/NK)/\sigma^2_p$$

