with the variance components defined as previously. These data suggest true four-year and one-year correlations of 0.85 and 0.91, respectively. Interpolating to 6 and 18 months, the true correlations in TOHP are estimated to be 0.92 and 0.90, respectively. Given three visits with three measurements each, we would expect to observe correlations of approximately 0.84 (6 months) and 0.83 (18 months). These figures lead to estimated variances for the change in means of 38.03 (standard error = 6.17) for 6 months and 40.41 (standard error = 6.36) for 18 months of observation.

Allocation of Subjects

Clinic-specific allocations are presented in Table 1.

Power_Calculations

Power calculations assume a two-sided test with significance level 0.05 and use the following formula:

Power =
$$1 - \Phi \left[z_{1-\alpha/2} - \frac{d}{\frac{\sigma^2}{n_1} + \frac{\sigma^2}{n_0}}\right]$$

where: $\Phi[\]$ = the area to the right of [] on the standard normal curve

 $z_{1-\alpha/2} = 1.96$

d = the difference in BP change between the intervention and comparison groups

 σ^2 = 6.172 for supplements and 6.362 for lifestyles

 n_1 = the number in the active intervention group

 n_0 = the number in the control group

The estimated powers associated with the expected numbers in the proposed study design are given in Table 12. All tests will have at least .90 power to detect a 2 mm Hg change in DBP.

POWER CALCULATIONS: SBP

Estimate of Variance

The same methods used for DBP have been used to estimate the components of variance for SBP. The variance of the mean BP (\vec{x}) at either baseline or termination can again be written as:

$$V_{(\vec{x})} = \sigma^2 = \sigma^2_p + \sigma^2_A/N + \sigma^2_e/NK$$

where: σ^2_{p} = between-person variance

 σ^2 A = between-visit variance

 σ^2 = within-visit variance

N = number of visits = 3

K = number of measurements per visit = 3

The variance of the difference between the baseline and termination values is a function of σ (defined above) and the tracking correlation (the variation in BP over time):

$$V(\overline{x}_1 - \overline{x}_2) = 2\sigma^2(1-\rho)$$

where:

- mean SBP at baseline

- mean SBP at termination

- the observed tracking correlation of the BP means over an average of 18 months of follow-up for the lifestyle interventions and six months of follow-up for the supplement interventions

Estimating the components of the variance of the mean BP at either base-1. line or termination

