Again, using estimates from Rosner and Polk (104) and from the HDFP (102):

$$\sigma^2 = 233.13$$

$$\sigma^{2}_{p} = 233.13$$
 $\sigma^{2}_{A} = 43.39$
 $\sigma^{2}_{e} = 13.16$

$$\sigma_{\rm e}^2 = 13.16$$

Therefore, $V(\bar{x})$, the estimated variance of the mean SBP (averaged over three visits with three readings per visit) at baseline or termination is 249.06.

2. Estimating the tracking correlation

> Estimates for 4-year tracking correlations come from data from Wales (103); estimates for 1-year tracking correlations come from Rosner and Polk (104). In addition, the relation between observed and true tracking correlations is estimated by the following equation:

$$\rho_{\text{true}} = \rho_{\text{obs}} \times (\sigma_{\text{p}}^2 + \sigma_{\text{A}}^2/N + \sigma_{\text{e}}^2/NK)/\sigma_{\text{p}}^2$$

For SBP, the observed and true tracking correlations are .67 and .83 for 4-years and .81 and .85 for 1-year, respectively. Interpolating to 6 and 18 months, the true correlations in TOHP are estimated to be .853 and .847. Given three visits with three measures each, we would expect to observe correlations of approximately .80 (6 months) and .79 (18 months). These figures lead to estimated variances for the change in means of 99.62 (standard error = 9.98) for 6 months of observation and 104.61 (standard error = 10.23) for 18 months of observation.

Allocation of Subjects

The same clinic-specific allocations shown in Table 1 are used.

Power Calculations

The estimated powers associated with the expected numbers are given in Table 13. All tests will have between .87 and .98 power to detect a 3 mm Hg change in SBP.

DATA ANALYSES

The data analyses will be performed by the CC, with input from other trial investigators, for review by the Data and Safety Monitoring Committee at its semi-annual meetings.

This study will allow for the evaluation of seven different interventions. For each intervention, baseline characteristics will first be examined in the intervention and comparison groups to see if randomization achieved equal allocation. The primary factors of interest are those to be affected by the trial, including DBP, body weight, dietary components, and exercise frequency. Other variables that might influence change in DBP will also be examined.

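### The observed four-year DBP correlation of 0.58 and the stated true value of 0.85 cannot both be right under the protocol's own formula, which gives 0.76

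*Protocol*

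**What the plan says.** Under Estimate of Variance in the Protocol's Power Calculations: DBP, the SD of change in DBP is built from three variance components and a tracking correlation. Two outside sources supply the correlation.

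- **Four years:** the Welsh study "suggests a correlation of 0.58 for DBPs taken four years apart". The protocol adds: "This was based on a single measurement at each point".
- **One year:** industrial-population data "suggest a one-year correlation of 0.85 for an average of 12 measurements taken at four visits with three measurements per visit".

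The section then gives a formula that turns an observed correlation into a true one, and states the result: "These data suggest true four-year and one-year correlations of 0.85 and 0.91, respectively". From these it interpolates true values of 0.92 (6 months) and 0.90 (18 months). It converts them to expected observed values of 0.84 and 0.83, and reaches change variances of 38.03 (SD 6.17) and 40.41 (SD 6.36). Table 12 and the claim of at least .90 power for 2 mm Hg rest on these SDs.

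The SBP section uses the same method and the same two sources: "For SBP, the observed and true tracking correlations are .67 and .83 for 4-years". Its one-year pair is .81 and .85.

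**The concern.** The step from 0.58 to 0.85 is too large. A single reading carries error from one visit and one measurement, so the correction is sizeable, but the printed components fix how sizeable. They do not take 0.58 as far as 0.85.

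The figure is used. It is one of the two anchor points for both interpolated correlations, and so it enters the SD of the primary endpoint for the lifestyle comparisons (18 months) and the supplement comparisons (6 months). A reader who follows the stated inputs and formula does not arrive at 6.36 or 6.17.

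**Working it through.** **Inputs** (Protocol, Power Calculations: DBP and SBP; Table 12). DBP components: between-person 109.11, between-visit 26.76, within-visit 7.42. Variance of a nine-reading mean: 118.85. Two-sided 0.05, difference 2 mm Hg.

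**Formula.** True correlation = observed × F(N, K), where F(N, K) = (between-person + between-visit/N + within-visit/NK) / between-person.

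**Step 1. The four conversions**

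| Conversion | N, K | F | Observed × F | Stated |
|---|---|---|---|---|
| DBP, 1 year | 4, 3 | 1.067 | 0.85 × 1.067 = 0.907 | 0.91 |
| SBP, 4 years | 1, 1 | 289.68/233.13 = 1.243 | 0.67 × 1.243 = 0.833 | .83 |
| SBP, 1 year | 4, 3 | 1.051 | 0.81 × 1.051 = 0.851 | .85 |
| DBP, 4 years | 1, 1 | 143.29/109.11 = 1.313 | 0.58 × 1.313 = **0.762** | **0.85** |

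Three of the four reproduce. The SBP four-year row uses the same source with the same N and K, so the formula is being read as the authors used it. Other readings of N and K for the DBP figure move further from 0.85: (1,2) gives 0.742, (1,3) 0.735, (3,3) 0.632 and (4,3) 0.619. Working backwards, 0.85/1.313 = 0.647.

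**Step 2. The plan's later figures, starting from 0.85 and 0.91**

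- Linear interpolation between 12 and 48 months: at 18 months 0.91 − 0.06 × 6/36 = 0.90; at 6 months 0.91 + 0.06 × 6/36 = 0.92.
- Divide by F(3,3) = 118.85/109.11 = 1.089: 0.83 and 0.84.
- Variance of change = 2 × 118.85 × (1 − correlation): 40.41 (SD 6.36) and 38.03 (SD 6.17).

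All match, so the printed SDs do come from 0.85.

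**Step 3. The same chain if 0.58 is right** (0.907 and 0.762, unrounded)

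| | 18 months | 6 months |
|---|---|---|
| True correlation | 0.907 − 0.145 × 6/36 = 0.883 | 0.907 + 0.145 × 6/36 = 0.931 |
| Expected observed | 0.810 | 0.855 |
| Variance of change | 45.1 (stated 40.41) | 34.5 (stated 38.03) |
| SD | 6.71 (stated 6.36) | 5.87 (stated 6.17) |

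Rounding the correlation to two decimals, as the plan does, gives 6.72 at 18 months and 5.97 at 6 months. Log-linear interpolation gives 6.74 and 5.83.

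**Step 4. Table 12.** Power = Φ(2/SE − 1.96) and detectable difference at 80% power = 2.8016 × SE, with SE = SD × √(1/n1 + 1/n0).

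| Row (n1/n0) | Printed | SD 6.36 | SD 6.71 |
|---|---|---|---|
| Sodium (327/416) | .99; 1.32 | .989; 1.32 | .981; 1.39 |
| Weight (308/232) | .95; 1.55 | .951; 1.55 | .929; 1.63 |
| Stress (242/319) | .92; 1.66 | .958; 1.52 | .938; 1.60 |

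Sodium and weight reproduce at 6.36. Stress does not: its printed detectable difference corresponds to an SD of 1.66/(2.8016 × 0.0852) = 6.95.

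The four supplement powers reproduce at SD 6.17. At 5.87 they become .959 (calcium), .955 (magnesium), .932 (potassium) and .927 (fish oil), against printed .94, .94, .91 and .90.

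**The case against.** A reader might infer that the 18-month SD is simply too small and all three lifestyle powers too favourable. The documents do not support that.

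- **Which number is wrong is unknown.** Everything after 0.85 reproduces. If 0.58 is a misprint for about 0.65, SD 6.36 and SD 6.17 stand and only the input needs correcting. This objection holds in full.
- **The stress row points the other way.** Its printed .92 and 1.66 are already less favourable than .94 and 1.60 at SD 6.71. It does not follow from 6.36 with 242/319, so it is a separate discrepancy in Table 12 and no evidence for this one.
- **No stated conclusion changes.** Every row stays at or above .90, and the supplement rows improve. Table 1 reports lifestyle numbers as already randomized, so no sample-size decision is open. This also holds.
- **6.71 may not be the SD in the enrolled cohort.** Entry requires a nine-reading DBP of 80-89 mm Hg, while the variance comes from a broader population. Assume bivariate normality and a restricted baseline variance of about 8.3 (roughly uniform over 10 mm Hg). The change variance is then (1 − r)² × 8.3 + 118.85 × (1 − r²), where r is the observed correlation. At 0.81 this gives about 41.2 (SD 6.42), close to the printed figure. But at 0.83 the same restriction gives about 37.2 (SD 6.10). It lowers both and does not make 0.85 follow from 0.58.
- **The replacement values depend on the interpolation.** The protocol names no method, and 6 months lies outside the one- and four-year anchors. The revised SDs are therefore approximate.

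**Conclusion.** The stated input, formula and result are inconsistent: 0.58 gives 0.76, and 0.85 needs about 0.65. That much rests only on figures in the protocol.

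The consequence is conditional on 0.58 being right and on linear interpolation. In that case the 18-month variance of change is about 12% larger (45.1/40.41 = 1.12) and the SD about 5.5% larger. Sodium loses about 1 point of power and weight about 2. Their detectable differences rise by 0.07-0.08 mm Hg. Supplement power was then slightly understated.

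The claim of at least .90 power holds either way. It would still hold for weight, at .90, under an assumed 10% loss in both groups (277/209), a rate that the protocol does not give.

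This is a faulty figure in the sample-size justification that should be corrected. It does not threaten the trial's ability to answer its questions.

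**What to change.** Check the four-year DBP correlation in the cited Welsh study, then do one of two things.

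- **If the source value is about 0.65:** correct 0.58 and leave 0.85, the SDs and the power figures derived from them.
- **If 0.58 is right:** replace 0.85 with 0.76, name the interpolation method, and recompute the 6- and 18-month correlations, both SDs and Table 12.

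Until this is settled, show sodium and weight power over SD 6.36-6.71: .99 to .98 and .95 to .93. Reconcile the stress row with its stated numbers and SD as a separate correction.

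The cost is one look-up and a few recomputed figures, slightly less favourable for sodium and weight if 0.58 stands. Nothing in the design or conduct of the trial changes.
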